8.4 Replacement of Withdrawn Patients

No replacement procedure of withdrawn patients is planned or accepted for this study.

9 TREATMENTS

9.1 Identification of Investigational Medicinal Products (IMPs)

Investigational medicinal products (IMPs) of this study are CetuGEX™ and the active comparator cetuximab.

In addition to CetuGEX™ or cetuximab, all patients will receive 5-FU and cisplatin or, in case of unacceptable toxicity, carboplatin. These drugs are non-investigational medicinal products (nIMPs) in this study and will be used according to general standard of care.

9.1.1 Investigational Medicinal Products

CetuGEX™

CetuGEX™ is a chimeric monoclonal glyco-optimized IgG antibody with fully human glycosylation. CetuGEX™ binds to the EGFR and shows an enhanced ADCC activity against tumor cells.

Name of the drug:	CetuGEX™
Active substance:	Chimeric monoclonal IgG antibody
Dosage form:	Solution for intravenous infusion, provided in single-use vials
Strength:	240 mg
Volume:	48 mL
Excipients:	Sodium citrate, sodium chloride, Tween 80, glycine, water for solution for infusion

CetuGEX™ will be manufactured in accordance with Good Manufacturing Practice (GMP) requirements by Glycotope Biotechnology, Heidelberg, Germany.

Cetuximab

Cetuximab, a chimeric monoclonal IgG antibody binding to the EGFR, will be the reference drug used in this study. The authorized product will be sourced from the European or US market as applicable and will be provided by Glycotope GmbH or its delegate for the European sites.

Name of the drug: Cetuximab
Active substance: Chimeric monoclonal IgG antibody
Dosage form: Solution for infusion, 2 mg/mL or 5mg/mL in vials with volumes as applicable for the corresponding market.

For more detailed information, please refer to the Summary of Product Characteristics (SmPC) for cetuximab¹¹.

9.1.2 Non-Investigational Medicinal Products

5-Fluorouracil

The chemotherapy drug 5-FU, a thymidylate synthase inhibitor, will be administered to all patients for the first line treatment phase (a maximum of 6 cycles).

Cisplatin (or, in case of unacceptable toxicity, Carboplatin)

The platinum-salt that will be used in this study is cisplatin. It will be administered as intravenous infusion for the first line treatment phase (maximum of 6 cycles) according to the routine standard of care at each site, avoiding corticosteroids as far as possible. If corticosteroids are required, dexamethasone is to be used (unless contraindicated). Carboplatin may be administered in the same fashion in case cisplatin is not tolerated and dose reduction of cisplatin is not deemed to be the appropriate measure. However, cisplatin is mandatory for the first therapy cycle.

9.2 Labeling and Packaging

9.2.1 Labeling

The medication labels for the IMPs and nIMP_s will comply with the requirements of local laws and regulations as well as with GMP Annex 13 and ICH-GCP. Master labels will be filed within the Trial Master File (TMF).

9.2.2 Packaging

The packaging and supply to the study sites of CetuGEX™ and cetuximab will be performed by Glycotope GmbH or a delegate company contracted and authorized by Glycotope GmbH.

9.3 Treatments Administered

The treatment period will consist of a first line treatment phase followed by maintenance therapy. CetuGEX™, cetuximab, 5-FU, cisplatin and carboplatin must be administered under the supervision of an investigator experienced in the use of antineoplastic medicinal products. Close monitoring is required during the infusion and for at least 1 hour after the end of the infusion. Availability of resuscitation equipment must be ensured.

Prior to the first infusion of cetuximab, patients must receive premedication with an antihistamine and dexamethasone (or another corticosteroid if dexamethasone is

contraindicated). According to the SmPC¹¹ this premedication is recommended prior to all subsequent infusions of cetuximab.

Prior to the first two infusions of CetuGEX™ (Day 0 and Day 1 of 990mg initial loading dose) patients must receive premedication consisting of paracetamol (acetaminophen) 1 g per os (PO) the evening before the infusion as well as paracetamol 1g PO, dexamethasone (or another corticosteroid if dexamethasone is contraindicated) and antihistamines approximately 60 minutes before the start of infusion. Premedication should be avoided during subsequent cycles. However, premedication might be applied after the occurrence of an IRR in relation to the previous infusion.

During administration of CetuGEX™/cetuximab, IRRs might occur. For a more detailed description of possible IRRs and dose adjustment procedures to be followed in case of IRRs, please refer to Section 9.9.

Combination Treatment Phase

Patients who fulfill all inclusion criteria and do not meet any of the exclusion criteria will be randomized in a 1:1 ratio to receive either CetuGEX™ or cetuximab in combination with 5-FU and cisplatin (or carboplatin later than the first cycle, in case of unacceptable toxicity), for a maximum of 6 chemotherapy cycles.

During the combination treatment phase, even if the chemotherapy is delayed for any reason (e.g., see Sections 9.9.3 and 9.9.4), the IMP (CetuGEX™ or cetuximab) administration may not be withheld and needs to be continued with weekly infusions as scheduled.

CetuGEX™

The study drug CetuGEX™ will be administered as infusion to all patients randomized to the CetuGEX™ arm, once weekly, starting with Day 0. Starting with the second infusion (Day 8 of Cycle 1), a time window of ± 1 day will be allowed for the weekly infusions (calculated from the previous infusion).

The initial dose will be 990 mg and subsequent doses will be 720 mg once weekly. The initial loading dose will be given as split-dose over 2 days with a priming dose of 60 mg on Day 0 diluted to a total volume of 100 mL (administered over 2 hours with a 30-minute break) and the remaining dose of 930 mg on Day 1 diluted to a total volume 500 mL (the intravenous infusion will last for approximately 4 hours). Infusion on Day 1 should be started within 24 ± 2 hours after start of infusion on Day 0. The exact timing, total volumes of infusions, steps for increasing infusion flow rates and duration of each flow rate for first and subsequent infusions can be found in Table 9-1. If clinically indicated, timely discontinuation of the infusion will be possible in order to prevent serious side effects.

Table 9-1: CetuGEX™ Infusion Scheme and Dosage

Infusion/Timing	Dose [mg] (Total Volume)	Duration [min]	Flow rate [(mL/h)]	Dose in mg/h
Infusion 1 (Cycle 1)	990			
Day 0	60 (100 mL)	60	35	21
		Break (30)	NA	
		60	65	39
Day 1	930 (500 mL)	30	20	37
		60	40	74
		≈ 164	165	306
Infusion 2* (Day 8 of Cycle 1)	720 (500 mL)	60	30	43
		60	55	79
		≈ 116	215	310
Infusion 3* (Day 15 of Cycle 1) and subsequent weekly infusions	720 (500 mL)	90	333	480

* Starting with the second infusion (Day 8 of Cycle 1), a time window of ± 1 day will be allowed for the weekly infusions (calculated from the previous infusion).

Cetuximab

Cetuximab will be administered once weekly as infusion to all patients randomized to the cetuximab arm. Starting with the second infusion (Day 8 of Cycle 1), a time window of ± 1 day will be allowed for the weekly infusions (calculated from the previous infusion). The initial dose will be 400 mg/m² body surface area (BSA) and each subsequent dose will be 250 mg/m² BSA. The maximum infusion rate for the initial dose must not exceed 5 mg/min. The maximum infusion rate for subsequent doses must not exceed 10 mg/min. The BSA will be calculated using the Mosteller formula:

$$BSA [m^2] = (\text{Weight [kg]} \times \text{Height [cm]}/3600)^{1/2}$$

The following information related to the infusion of CetuGEX™ and cetuximab will be recorded for each infusion:

- Infusion start time
- Infusion stop time
- Time, duration and reason of any infusion interruptions, if applicable
- Adjustments to infusion rate, if applicable

Concomitant Platinum-based Chemotherapy

During the combination treatment phase, all randomized patients will receive 5-FU as continuous intravenous infusion, in combination with cisplatin (or carboplatin in case of required substitution of cisplatin in further cycles). This platinum-based chemotherapy will be administered for a maximum of 6 cycles of 3 weeks each, starting approximately 1 hour after CetuGEX™/cetuximab infusion on Day 1 of each cycle. If the CetuGEX™/cetuximab infusion is administered in the afternoon, the concomitant

platinum-based chemotherapy may be administered the next morning; however, all drugs should be given within 24 hours.

5-fluorouracil will be administered in doses of 1000 mg/m² BSA per day every 3 weeks (one cycle of cisplatin or carboplatin treatment) as continuous intravenous infusion on Days 1 to 4 of each cycle.

Cisplatin will be administered as a dose of 100 mg/m² BSA by infusion every 3 weeks, on Day 1 of each cycle, according to current standards and prescribing guidelines including hydration before and after cisplatin treatment, as required (please refer to the instructions in the corresponding SmPC [Appendix F]). In case cisplatin has to be replaced by carboplatin for toxicity reasons, Carboplatin will be administered at an area under the curve (AUC) of 5 mg/mL/min (using the Calvert formula for calculation¹²) as a 1-hour intravenous infusion every 3 weeks, on Day 1 of each cycle. As per SmPC (Appendix H), carboplatin may not be used in patients with bleeding tumors.

In case of related relevant toxicity, each compound of the chemotherapy treatment can be discontinued prior to completion of 6 cycles of chemotherapy, and patients will continue with the remaining compounds of the combination therapy. After all chemotherapy has been discontinued, irrespective if the 6 cycles are completed or discontinued prematurely for any other reason apart from progression, patients will directly enter the maintenance phase.

Single-Agent Maintenance Treatment Phase

After completion or discontinuation of chemotherapy for any other reason apart from progression, the treatment will be followed by maintenance therapy receiving CetuGEX™ alone or cetuximab alone, respectively. Single-agent maintenance therapy will be continued with unchanged dosing schedule until progression of disease or limiting toxicity.

9.4 Dispensing and Storage

The IMPs and nIMPs supplied by Glycotope GmbH are to be used exclusively in the clinical study according to the instructions of this protocol. The investigator and the dispensing study team member(s) are responsible for dispensing the study medications according to the dosage scheme and for ensuring proper storage of the IMPs and nIMPs. The study medication and the nIMPs will be administered at the study site, under strict surveillance of experienced study team members.

All study medication must be stored in accordance with the manufacturer's instructions and separately from normal hospital/practice stocks in a securely locked area, only accessible to authorized study personnel.

CetuGEX™ and cetuximab have to be stored by 2-8°C and should not be frozen.

5-fluorouracil and cisplatin have to be stored at 15-25°C and protected from light.

Carboplatin has to be stored not exceeding 25°C and protected from light.

Dispensing will only be performed by authorized study team members and according to the interactive web response system (IWRS) for randomization. IWRS will be performed

by Perceptive. Receipt and dispensing of study medication must be recorded by an authorized person at the investigator's site.

Detailed instructions concerning the storage, preparation and administration of IMPs and nIMP will also be described in a separate Drug Handling Manual.

All unused study medication should be returned to Glycotope GmbH or its designee for destruction or can be destroyed at the study site upon sponsor's request after the drug accountability check has been performed.

9.5 Method of Assigning Patients to Treatment Groups

Patients eligible for study participation will be randomized using a 1:1 ratio to either the CetuGEX™ or cetuximab arm. The randomization may take place within 3 days prior to Day 0 of the first treatment cycle for the patients randomized in CetuGEX™ arm or prior to Day 1 of the first treatment cycle.

Randomization will be stratified by:

- FcγRIIIa status (FF or FV or VV)
- Oral cavity and oropharynx vs. other locations
- Locally recurrent vs. metastatic disease
- EGFR treatment naïve vs. EGFR treatment as part of multimodal therapy

A centralized randomization procedure the IWRS will be used assigning a unique randomization number to each patient.

9.6 Blinding and Unblinding Treatment Assignment

Blinding at the level of study treatment does not apply since the study will be open label.

9.7 Selection of Doses in the Study

Doses for cetuximab, 5-FU, cisplatin and carboplatin are chosen based on routine standard of care and according to the instructions of the corresponding SmPCs and product information leaflets for the treatment of SCCHN.

The dosage of CetuGEX™ has been chosen based on the results of former studies and PK simulations, indicating that an initial dose of 990 mg followed by subsequent infusions of 720 mg are well tolerated and safe.

9.8 Selection of Timing of Dose for Each Patient

Timing of dose for each patient has been chosen according to current standard of care and based on the instructions in the corresponding SmPCs and product information leaflets. According to the instructions for treatment of recurrent or metastatic SCCHN, platinum-based chemotherapy in combination with 5-FU should not start prior to 1 hour after end of cetuximab. The same timing has been chosen for CetuGEX™. The platinum-based chemotherapy should be given within 24 hours after the infusion of

CetuGEX™/cetuximab. Administration of 5-FU should be started within 24 hours after the infusion of CetuGEX™/cetuximab.

9.9 Dose Adjustment Criteria

Adjustment of the study drug doses is performed according to the rules described in this section.

[figure not shown]
Mild or moderate IRRs are very common comprising symptoms such as fever, chills, dizziness, or dyspnea that occur in a close temporal relationship mainly to the first CetuGEX™/cetuximab infusion.

Severe IRRs also may commonly occur, in rare cases with fatal outcome.

In case of IRRs requiring dose adjustment, this should be performed as described in following sections.

The dose of CetuGEX™/cetuximab will be adjusted for CetuGEX™/cetuximab-related grade 3 skin toxicities only as displayed in Figure 9-1 and described in sections 9.9.1 and 9.9.2. CetuGEX™/cetuximab therapy will not be withheld for chemotherapy-related toxicities.

Figure 9-1: Treatment Modification in the Event of Grade 3 Skin Toxicity Considered to be Related to Weekly Administration of CetuGEX™/Cetuximab.

9.9.1 CetuGEX™

There were no severe IRRs in the Phase 1 study of CetuGEX™. It was also noted that decreasing the infusion rate did not influence the symptom control of mild to moderate IRRs. At this time it is recommended that CetuGEX™ infusions should be temporarily interrupted where necessary until improvement.

Whilst no severe IRRs have occurred to date in early clinical trials with CetuGEX™, it should be noted that severe IRRs may occur, in rare cases with fatal outcome, and investigators should be vigilant of similar reactions like observed for cetuximab (see Section 9.9.2).

In case of a severe IRR, the CetuGEX™ infusion needs to be discontinued immediately, and infusion tubing has to be disconnected from the patient. Emergency treatment (epinephrine, broncho-dilators, antihistamines, glucocorticoids, intravenous fluids, vasopressor agents, oxygen, etc., as medically indicated) might be necessary.

Patients must be withdrawn immediately from the treatment and must not receive any further CetuGEX™ treatment.

Skin toxicities: If a patient experiences a grade 3 skin toxicity (as defined in the US NCI-CTC, Version 4.0), CetuGEX™ therapy may be skipped for up to two consecutive infusions without changing the dose level. Patients with grade ≥ 3 reactions should be referred to the dermatologist for advice and management. If the toxicity resolves to grade 2 or less by the following treatment period, treatment may resume. With the second and third occurrences of grade 3 skin toxicity, CetuGEX™ therapy may again be skipped for up to two consecutive infusions, with concomitant dose reductions to 600 mg and 480 mg, respectively. CetuGEX™ dose reductions are permanent. Patients should discontinue CetuGEX™ if more than two consecutive infusions are withheld or a fourth occurrence of grade 3 skin toxicity occurs despite appropriate dose reduction.

Table 9-2: Treatment Adjustment in the Event of CetuGEX™ Caused Allergic/Hypersensitivity Reaction

CTC Grade Allergic/Hypersensitivity Reaction	Treatment CetuGEX™
Grade 1	Infusions should be temporarily interrupted where necessary until improvement of mild IRRs.
Grade 2	Infusions should be temporarily interrupted where necessary until improvement of moderate IRRs.
Grade 3 or Grade 4	
Stop the CetuGEX™ infusion immediately and disconnect infusion tubing from the patient. Administer epinephrine, broncho-dilators, antihistamines, glucocorticoids, intravenous fluids, vasopressor agents, oxygen, etc., as medically indicated.
 
Patients must be withdrawn immediately from the treatment and must not receive any further CetuGEX™ treatment.

9.9.2 Cetuximab

In case of mild to moderate IRRs, the infusion rate of cetuximab might be decreased and it is recommended to maintain the reduced infusion rate for all subsequent infusions.

During treatment with cetuximab, severe IRRs usually develop during or within 1 hour of the initial infusion, but may occur after several hours or with subsequent infusions. Although the underlying mechanism has not been identified, some of these reactions may be anaphylactoid/anaphylactic in nature and may include symptoms such as bronchospasm, urticaria, increase or decrease in blood pressure, loss of consciousness or shock. In rare cases, angina pectoris, myocardial infarction or cardiac arrest have been observed.

In case of severe IRRs (grade 3 and 4), the cetuximab infusion requires immediate and permanent discontinuation and emergency treatment might be necessary.

Skin toxicities: In case of skin toxicities like grade 1 or 2 acne –like rash, pruritus or dry skin due to cetuximab treatment, events should be treated according to the instructions given in the cetuximab SmPC (Appendix E). If a patient experiences a grade 3 skin toxicity (as defined in the US NCI-CTC, Version 4.0), cetuximab therapy may be skipped for up to two consecutive infusions without changing the dose level. Patients with grade ≥ 3 reactions should be referred to the dermatologist for advice and management.

With the second and third occurrences of grade 3 skin toxicity, cetuximab therapy may again be skipped for up to two consecutive infusions (one infusion during maintenance) with concomitant dose reductions to 200 mg/m² and 150 mg/m² respectively. Cetuximab

dose reductions are permanent. Patients should discontinue cetuximab if more than two consecutive infusions are withheld or a fourth occurrence of grade 3 skin toxicity occurs despite appropriate dose reduction (see Figure 9-1).

Allergic/hypersensitivity reactions: In each case of allergic/hypersensitivity reaction, the investigator should implement treatment measures according to the best available medical practice. Based on previous experience with cetuximab allergic/hypersensitivity reactions, the treatment guidelines as described in Table 9-3 may be applicable.

Table 9-3: Treatment Adjustment in the Event of Cetuximab Caused Allergic/Hypersensitivity Reaction

CTC Grade Allergic/ Hypersensitivity Reaction	Treatment
Grade 1	Decrease the cetuximab infusion rate by 50% and monitor closely for any worsening. The total infusion time for cetuximab should not exceed 4 hours.
Grade 2	Stop cetuximab infusion. Administer bronchodilators, oxygen, etc. as medically indicated. Resume infusion at 50% of previous rate once allergic/hypersensitivity reaction has resolved or decreased to Grade 1 in severity, and monitor closely for any worsening
Grade 3 or Grade 4	Stop the cetuximab infusion immediately and disconnect infusion tubing from the patient. Administer epinephrine, broncho- dilators, antihistamines, glucocorticoids, intravenous fluids, vasopressor agents, oxygen, etc., as medically indicated. Patients must be withdrawn immediately from the treatment and must not receive any further cetuximab treatment.

Retreatment following allergic/hypersensitivity reactions: Once a cetuximab infusion rate has been decreased due to an allergic/hypersensitivity reaction, it will remain decreased for all subsequent infusions. For patients having a second allergic/hypersensitivity reaction with the slower infusion rate, the infusion should be stopped, and the patients should be removed from the study. If a patient experiences a Grade 3 or 4 allergic/hypersensitivity reactions at any time, cetuximab should be discontinued.

If therapy must be withheld for a longer period of time than defined above, the patient will be removed from the study treatment. In special cases, the investigator may request that the patient continues to receive cetuximab (the investigator must ask permission from the legal representative of the sponsor).

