8.3 Premature Patient Withdrawal

All patients will be advised that they are free to withdraw from participation in this study at any time, for any reason, and without prejudice. Every reasonable attempt should be made by the investigator to keep patients in the study; however, patients must be withdrawn from the study if they withdraw consent to participate. Investigators must attempt to contact patients who fail to attend scheduled visits by telephone or other means to exclude the possibility of an AE being the cause of withdrawal. Should this be the cause, the AE must be documented, reported, and followed as described in Section 11.2.

The sponsor reserves the right to request the withdrawal of a patient due to protocol violations or other reasons.

The investigator also has to withdraw patients from the study at any time for the following reasons:

- Unacceptable toxicity
- More than 3 weeks delay of scheduled infusion of CetuGEX™/cetuximab (i.e., missing more than 2 consecutive infusions)
- Intercurrent illness interfering with study procedures
- Noncompliance with study procedures, or
- Pregnancy.

If a patient is withdrawn from treatment prior to PD due to unacceptable toxicity or any other reasons as detailed above except noncompliance with study procedures, the patient will remain on regular study schedule until progression of disease unless this might interfere with the patient's best interest.

If a patient is withdrawn from the complete study before documented progressive disease, the reason for withdrawal and the date of discontinuation will be recorded on the appropriate electronic case report form (eCRF). Whenever possible, the evaluations that were to be conducted at the Final Examination should be performed at the time of premature discontinuation.

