10.3.1.2 Assessment of Secondary Efficacy Endpoints

Tumor assessments performed by the investigator and by independent centralized reading as described in detail above will also be used for evaluation of secondary efficacy endpoints.

Progression-free Survival assessed by Centralized Read

Tumor images to determine PFS as assessed by independent centralized reading will be evaluated as described in detail in Section 10.3.1.1.

Objective Response Rate and Duration of Response

Objective response rate is the portion of patients with a tumor size reduction of a predefined amount for a minimum time period and it is defined as the sum of partial responses and complete responses. Response duration is measured from the time of initial response until documented tumor progression.

The investigator and independent centralized reader will evaluate whether complete response (CR), partial response (PR), stable disease (SD) or progressive disease (PD) has occurred, according to the criteria presented in Appendix C:

Best Overall Response Rate

The best overall response rate is the best response (CR, PR or SD) recorded per patient from the start of the treatment until disease progression/recurrence. Separate rates per CR, PR or SD as best response will be evaluated.

Clinical Benefit Rate

The clinical benefit rate is the portion of patients with an objective response or stable disease.

Overall Survival

The overall survival is defined as the duration of time from randomization to the time of death. The patients will be followed up by monthly phone calls until death or for a maximum duration of 24 months after randomization of the last patient for assessment of OS.

Time to Treatment Failure

Time to treatment failure is defined as the time from randomization to treatment discontinuation for any reason, including disease progression, treatment toxicity, patient preference, or death.

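### An exception to the antibody-withholding limit exists for cetuximab only, without criteria, so the discontinuation that counts as a TTF event is triggered differently in the two arms

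*Protocol*

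**What the plan says.** **The common rule.** Protocol 8.3 introduces its list of withdrawal reasons with "The investigator also has to withdraw patients from the study at any time for the following reasons". One item is a delay of more than three weeks in the antibody, explained as missing more than two consecutive infusions. It names CetuGEX and cetuximab together and mentions no exception.

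**The arm-specific sections.** Protocol 9.9.1 has CetuGEX stopped "if more than two consecutive infusions are withheld or a fourth occurrence of grade 3 skin toxicity occurs". Protocol 9.9.2 matches it: "Patients should discontinue cetuximab if more than two consecutive infusions are withheld".

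**The exception.** At the end of 9.9.2, under retreatment after allergic/hypersensitivity reactions, the protocol says: "If therapy must be withheld for a longer period of time than defined above, the patient will be removed from the study treatment". It then adds: "In special cases, the investigator may request that the patient continues to receive cetuximab", and in brackets that "the investigator must ask permission from the legal representative of the sponsor". Section 9.9.1 has no counterpart.

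**The endpoint.** Protocol 10.3.1.2: "Time to treatment failure is defined as the time from randomization to treatment discontinuation for any reason". SAP 7.2 derives TTF from the discontinuation date, and SAP 9.2.3 compares the arms with an unstratified log-rank test. The trial is open label (protocol 9.6).

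**The concern.** TTF has one definition for both arms, but its event depends on the rule that ends treatment. For over-long withholding, that rule is mandatory in one arm and can be waived in the other. The waiver is requested and granted with the arm known, against no written criteria. A difference in TTF, or in exposure, could then partly reflect how often exceptions were granted.

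The scope of the exception is also unclear. It refers back to a period defined earlier, but the retreatment paragraph defines none. The only withholding period in 9.9.2 is the skin-toxicity limit, which belongs to a different kind of event. Sites could apply the exception to different situations, and an analyst could not say which patients were eligible for it.

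**Working it through.** **Step 1: the rules side by side**

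| Rule | CetuGEX | Cetuximab |
|---|---|---|
| Stop after more than two consecutive missed infusions (8.3; 9.9.1 / 9.9.2) | yes | yes |
| Continuation past the limit with sponsor permission | none stated | 9.9.2, no criteria |
| Removal after a second allergic reaction at the slower infusion rate | none stated | 9.9.2 |
| Tighter skipping allowance (one infusion) in maintenance, second and third grade 3 skin events | none stated | 9.9.2 |

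Row 2 can only lengthen cetuximab TTF. Row 3 shortens it. Row 4 could shorten it, if exceeding the allowance counts as withholding beyond the defined period. Figure 9-1 was not readable in the copy reviewed.

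**Step 2: the plan's own figure.** The only powered figure is 192 PFS events (protocol 13.2). With two-sided 0.05 and 80% power, Schoenfeld gives 4(1.960 + 0.842)² / (ln HR)² = 191 at HR 2/3 (5.6/8.4) and 196 at HR 0.67. The 192 reproduces, and this point does not change it. No power or median is stated for TTF, so the sizes below rest on assumptions.

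**Step 3: stops only postponed.** Assume exponential TTF, no true difference, median m of 4 or 5.6 months, a share s of cetuximab patients granted the exception, and discontinuation delayed by k weeks. Comparing mean times gives

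rate ratio (CetuGEX/cetuximab) = 1 + s × (7k/30.4375) / (m/ln 2)

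- Smallest case: s = 1%, k = 4, m = 5.6. 1 + 0.01 × 0.920/8.079 = 1.001.
- Largest case: s = 10%, k = 12, m = 4. 1 + 0.10 × 2.760/5.771 = 1.048.

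**Step 4: stops removed for good.** Borrow the PFS medians as background hazards: control ln 2/5.6 = 0.1238 per month, CetuGEX ln 2/8.4 = 0.0825. Suppose over-long withholding would end treatment first in a share p of controls. Its hazard is then μ = 0.1238 × p/(1 − p), taken as equal in both arms. If a fraction w of the control stops is waived permanently,

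HR = (0.0825 + μ) / (0.1238 + (1 − w)μ)

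| p | μ | w = 0 | w = 1/4 | w = 1 |
|---|---|---|---|---|
| 2% | 0.0025 | 0.673 | 0.677 | 0.687 |
| 5% | 0.0065 | 0.683 | 0.692 | 0.719 |
| 10% | 0.0138 | 0.700 | 0.718 | 0.778 |

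The table uses unrounded hazards. Both calculations isolate the exception and leave out rows 3 and 4. Taken alone, it works against CetuGEX.

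**The case against.** The case against giving this much weight has several parts.

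- **Rarity.** The exception is for special cases, so waiving every qualifying patient for good is an extreme. This stands: the last column of the second table is an upper end, not an expectation.
- **Direction.** A reader might infer that TTF is biased in favour of cetuximab. The documents do not support that, because the other cetuximab-only rules act in the opposite direction.
- **Refusal.** A reader might also infer that refusing permission shortens cetuximab TTF. It does not. Refusal leaves in force the same limit that CetuGEX patients have.
- **Grade 3 or 4 reactions.** It is tempting to read the exception as overriding that stop. The exception follows a sentence about therapy being withheld, whereas a grade 3 or 4 reaction ends therapy. Section 9.9.2 says so in its text, in Table 9-3 ("Patients must be withdrawn immediately from the treatment and must not receive any further cetuximab treatment") and again in the retreatment paragraph. The placement merits one clarifying sentence and no more.
- **Sponsor discretion elsewhere.** In either arm the sponsor may request withdrawal (8.3) and decides on continuation when treatment of an adverse event departs from protocol (11.2.4). Neither provision addresses the withholding limit, so neither gives CetuGEX an equivalent route. Nothing in the documents shows that permission would be guided by a patient's outcome.
- **Existing safeguards.** SAP 8.4 tabulates delays and interruptions with reasons, SAP 8.2 lets data review classify further issues as major violations, and TTF is repeated in the per-protocol population. This helps only in part. Continuing past a stopping rule is not among the listed criteria, and excluding such patients does not answer the intention-to-treat question.
- **Different products.** Two antibodies may justify different management. This stands, so identical wording in both arms is not required.

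**Conclusion.** The inconsistency is real. A limit that is mandatory in both arms in 8.3 can be waived in one arm in 9.9.2, without criteria and with an unclear reference period, and it feeds a log-rank-tested secondary endpoint. The net direction of any bias in TTF cannot be determined.

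The effect of the exception alone is probably small unless exceptions are common: a rate ratio of about 1.00 to 1.05 in place of 1 when stops are postponed, and a hazard ratio of 0.78 in place of 0.70 at the extreme. These sizes rest on exponential times, assumed frequencies and, in the second case, PFS medians standing in for TTF.

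A reader might carry the point over to the primary endpoint. The documents do not support a direct effect. PFS does not count discontinuation as an event, and under 8.3 patients withdrawn from treatment generally stay on the study schedule until progression. Only indirect routes remain, through exposure or through censoring at new anticancer treatment (SAP 7.2). This should be corrected, but it does not threaten the trial's main conclusion.

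**What to change.** 1. **Protocol.** Reconcile 8.3, 9.9.1 and 9.9.2 so that the discontinuation rule and any exception agree across sections and arms, or justify the arm difference. State which withholding period the exception refers to and settle its relation to the grade 3 or 4 stop. The clinical team decides which rule is kept.
2. **eCRF.** Record each exception requested and granted, with date and reason.
3. **SAP 9.2.3.** Add a TTF sensitivity analysis that dates failure at the day the stopping criterion was met, in either arm, whether or not an exception was granted. Infusion records already collected for the exposure analysis (SAP 8.4) should allow missed consecutive infusions to be identified.

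The cost is a short amendment to the protocol text, one eCRF item and one additional TTF run. Sample size and the primary analysis do not change.
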